#### **4.7.3.1.3 Assessment of Severity**

The investigator will assess the severity of each AE using the following scale:

- **Mild:** The subject is aware of the AE but is still able to perform all activities; minimal or no medical intervention or therapy is required.
- **Moderate:** The subject has to discontinue some activities due to the AE; minimal or no medical intervention or therapy is required.
- **Severe:** The subject is incapacitated by the AE and is unable to perform normal activities; significant medical intervention or therapy is required, and hospitalization is possible.

#### **4.7.3.1.4 Assessment of Causality**

The investigator will assess the causal relationship/relatedness of each AE to the study drug using the following scale:

- **Not Related:** Onset of the AE has no reasonable temporal relationship to administration of the study drug, a causal relationship to administration of the study drug is biologically implausible, or the event is attributed to an alternative etiology.
- **Unlikely Related:** Onset of the AE has a reasonable temporal relationship to study drug administration and although a causal relationship is unlikely, it is biologically plausible.
- **Possibly Related:** Onset of the AE has a strong temporal relationship to administration of the study drug, cannot be explained by the subject's clinical state or other factors, and a causal relationship is biologically plausible.
- **Probably Related:** Onset of the AE shows a distinct temporal relationship to administration of the study drug that cannot be explained by the subject's clinical state or other factors, the AE is a known reaction to the product or chemical group, or can be predicted by the product's pharmacology.

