#### **4.1.2 Risk/Benefit**

Subjects will be informed that participation in a human PK study like the present one cannot be of benefit to healthy volunteers. Nevertheless, the information from the physical examination, vital sign measurements, and ECG results may be shared with the subject's personal physician if this is the subject's choice. Subjects will be informed that it is also their choice to inform their personal physician that they are participating in this research study.

Subjects will be informed that their contribution to the study is of major importance to agencies like the FDA to understand if and how much NDMA is produced from ranitidine in the human body. However, since this is a study involving healthy volunteers, subjects will be informed that they have the option not to participate.

Subjects will be informed that they may be exposed to risks associated with the pharmacological properties of the study drug and the study procedures. The following summary of potential AEs for ranitidine 300 mg will be provided to and discussed with the subjects:

- Headache, sometimes severe, is the most common adverse effect. The following additional adverse events have been reported in patients taking ranitidine, but whether they were caused by ranitidine has been unclear in many cases:
  - Neurological effects: Rarely malaise (general discomfort), dizziness, somnolence (sleepiness), insomnia (difficulty sleeping), vertigo (dizziness). Rare cases of reversible mental confusion, agitation, depression, hallucinations mainly in severely ill elderly patients, reversible blurred vision, or reversible involuntary motor disturbances.
  - Heart effects: Rare reports of abnormal heart rhythms.
  - Abdominal effects: Constipation, diarrhea, nausea/vomiting and abdominal discomfort/pain. Occasional reports of hepatitis (liver inflammation). Rare cases of liver failure or pancreatitis (inflammation of pancreas).
  - Musculoskeletal effects: Rare reports of arthralgias (joint pain) and myalgias (muscle aches).
  - Blood/vessel effects: Leukopenia, granulocytopenia and thrombocytopenia (decreased blood cell counts) in a few patients. Rare cases of vasculitis (blood vessel inflammation), agranulocytosis or pancytopenia (more severe decreased blood counts), and exceedingly rare cases of acquired immune hemolytic anemia (low red blood cell count).

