  - Sexual effects: Controlled studies have shown no hormone effects, however, occasional cases of impotence (erectile dysfunction), and loss of libido (sex drive) in males, but the rates did not differ from that in the general population. Rare cases of breast symptoms and conditions, including galactorrhea (milky nipple discharge) and gynecomastia (enlarged breast tissue).
  - Skin/hair effects: Rash, including rare cases of erythema multiforme (skin or mouth lesions). Rare cases of alopecia (hair loss).
  - Lung effects: Potential increased risk of pneumonia (lung infection).
  - Other: Rare cases of hypersensitivity reactions (exaggerated immune response that can cause trouble breathing, fever, rash or increased blood counts), anaphylaxis (severe allergic reaction), angioneurotic edema (swelling under the skin), acute interstitial nephritis (kidney inflammation), and small increases in serum creatinine (effect on kidneys).

In addition, subjects will be informed the purpose of this study is to evaluate whether ranitidine administration results in increased NDMA levels in urine and plasma. Subjects will be informed that NDMA is classified as a probable known carcinogen, however the ranitidine that subjects take in this study has been tested and shown to be well below the acceptable limits and these

levels are stable on repeated testing. At the acceptable limit, there is approximately a 1 in 100,000 chance of cancer after 70 years of exposure to that level.

The study drugs will not be administered to anyone who is pregnant. All women must take a pregnancy test before receiving any study drug in this study. All women of childbearing potential enrolled on this study will be informed that they must use effective birth control methods (abstinence, intrauterine device, and contraceptive foam and a condom [i.e., double-barrier method]) during treatment. Subjects will be informed that they must notify the investigator if they or their female partners become pregnant during the course of the study.

Subjects will be informed that insertion of an IV catheter may be required for blood sample collection and, during insertion of the catheter, soreness, bruising, or infection at the insertion site are possible but unlikely. Subjects will also be informed that dizziness and lightheadedness may occur during direct venipuncture, insertion of the IV catheter, or during blood collection.

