## 4.2.2 Exclusion Criteria

Subjects who meet any of the following exclusion criteria will not be eligible to participate in the study:

1. Subject has used antacids or proton pump inhibitors within 14 days of screening (interferes with *H. pylori* testing).
2. Subject has used any prescription or nonprescription drugs (including antacids, proton pump inhibitors, aspirin or NSAIDs and excluding oral contraceptives and acetaminophen) within 14 days or 5 half-lives (whichever is longer) or complementary and alternative medicines within 28 days before the first dose of study drug.
3. Subject is currently participating in another clinical study of an investigational drug or has been treated with any investigational drug within 30 days or 5 half-lives (whichever is longer) of the compound
4. Subject has used nicotine-containing products (e.g., cigarettes, cigars, chewing tobacco, snuff) within 6 weeks of Screening
5. Subject has consumed alcohol, xanthine-containing products (e.g., tea, coffee, cola), caffeine, grapefruit, or grapefruit juice within 24 h of check-in. Subjects must refrain from ingesting these throughout the study. Subjects must also refrain from using mouthwash from check-in until check-out.
6. Subject has a history or evidence of a clinically significant disorder, condition, or disease (e.g., cancer, human immunodeficiency virus [HIV], hepatic or renal impairment) that, in the opinion of the investigator would pose a risk to subject safety or interfere with the study evaluation, procedures, or completion. This includes subjects with any underlying medical conditions that put subjects at higher risk for coronavirus disease of 2019 (COVID-19) complications; per current Center for Disease Control and Prevention recommendations this includes:
  - People with chronic lung disease or moderate to severe asthma
  - People who have serious heart conditions
  - People who are immunocompromised
  - Many conditions can cause a person to be immunocompromised, including cancer treatment, smoking, bone marrow or organ transplantation, immune deficiencies, poorly controlled HIV or AIDS, and prolonged use of corticosteroids and other immune weakening medications
  - People with severe obesity (body mass index [BMI] of 40 or higher)
  - People with diabetes
  - People with chronic kidney disease undergoing dialysis
  - People with liver disease

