#### **4.7.3.1.2 Adverse Event Reporting**

The recording of AEs will begin after the subject signs the informed consent form and will continue until discharge (or early termination). All AEs, whether serious or nonserious and whether or not related to the study drug, must be recorded in the eCRF. Study subjects will be instructed to warn study staff if he or she has any unexpected symptoms. In addition, all subjects will receive a reminder telephone call approximately 24 h before Check-in.

Any SAE (whether expected or unexpected) must be entered into the eCRF system and reported by email to the medical monitor or designee using the SAE Reporting Form within 24 h of the investigator or study clinic staff becoming aware of the event. It is the responsibility of the investigator to report all SAEs to the medical monitor, to provide the most complete report possible, and to assess each SAE for its relationship to the study drug. The investigator is responsible for obtaining follow-up information on all SAEs and submitting follow-up SAE data. Any unexpected SAEs must be reported promptly to the investigator's IRB as per the IRB's requirements.

In the event of a fatal or life-threatening SAE, the sponsor will notify the appropriate FDA authorities within 7 calendar days of receipt of the report. The sponsor will follow all 7-day alert reports with a written report within 10 working days of receipt of the case. Serious AE cases that concern nonfatal, nonlife-threatening events that are unexpected and at least possibly related to the study drug will be submitted in writing to the FDA within 10 working days of receipt.

Furthermore, any AEs that are not expected, occur at a higher frequency, or would require modification of the study protocol and/or informed consent must be reported to the FDA within 10 working days.

Adverse events that are assessed by the investigator as possibly or probably related to the study drug will be followed until they resolve or stabilize. All SAEs will be followed until resolution.

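### The causality scale bars Possibly Related whenever another explanation exists, so a plausible drug event with a competing cause has no clear level and, if non-serious, can lose its required follow-up

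*Protocol*

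**What the plan says.** Protocol section 4.7.3.1.4 gives the investigator four levels of relatedness.

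- Not Related: the timing does not fit, or a causal link is implausible, or the event is put down to another cause.
- Unlikely Related: "Onset of the AE has a reasonable temporal relationship to study drug administration and although a causal relationship is unlikely", the link is still plausible.
- Possibly Related: the event has a "strong temporal relationship to administration of the study drug, cannot be explained by the subject's clinical state or other factors", and a causal link is plausible.
- Probably Related: distinct timing with the same no-other-explanation wording, followed by two further criteria (a known reaction, or one predictable from the pharmacology) in a list closed by an or.

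Two rules in section 4.7.3.1.2 use the grade. Adverse events "assessed by the investigator as possibly or probably related to the study drug will be followed until they resolve or stabilize". Serious events that are neither fatal nor life-threatening and are "unexpected and at least possibly related to the study drug will be submitted in writing to the FDA" have 10 working days for the report. The grade also enters the summaries of treatment-emergent events by relationship (Protocol section 4.9.8.1; SAP section 7.5.1).

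**The concern.** A middle level such as Possibly Related usually holds events for which the drug is a real candidate but not the only one. Here that level is closed to them, because it demands that nothing else explain the event. The scale then has no clear place for a common kind of safety observation, and two investigators can grade the same event differently while both follow the text.

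This matters because the grade is more than descriptive. For some events it decides whether follow-up is required, and it decides which row of the relatedness table the event enters.

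**Working it through.** No arithmetic is involved in the main check, and the plan states no figure to reproduce. The check takes one event through the four definitions, then sets each follow-up and reporting rule against the grade.

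**Step 1. The test event.** Take dizziness that begins soon after a dose and close to a blood draw. Section 4.1.2 lists dizziness among the effects reported with ranitidine (as rare, with causation often unclear). It also warns that "dizziness and lightheadedness may occur during direct venipuncture", catheter insertion or blood collection. Section 4.7.1.1 schedules draws at 0.5, 1, 1.5 and 2 h after dosing, among others, so an onset near a draw can also be near a dose.

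**Step 2. The event against each level.**

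- Possibly Related: timing met, plausibility met, no-other-explanation condition failed. Barred.
- Probably Related, criteria read as joint: fails on the same condition. Barred.
- Probably Related, criteria read as alternatives: a known reaction is enough, so the event qualifies. It is then barred from the lower level and admitted to the higher one.
- Unlikely Related: the definition requires that "although a causal relationship is unlikely, it is biologically plausible". An investigator who regards the drug as a real candidate has not judged causality unlikely. No clear fit.
- Not Related: available only if the event is attributed to another cause. The text does not say how firm that attribution must be, so an ambiguous event can be placed here.

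On neither reading of Probably Related does the event reach Possibly Related. For an event that is neither a known nor a predictable reaction, the alternative reading gives no help, since only the timing criterion remains and it carries the same condition.

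**Step 3. Which rules depend on the grade.**

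Follow-up (sections 4.5 and 4.7.3.1.2):

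- Events graded possibly or probably related, until resolved or stable: depends on the grade.
- All serious events, until resolution: does not.
- Events leading to discontinuation, until resolved or stable: does not.

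One of three depends on the grade.

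Recording and reporting (section 4.7.3.1.2):

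- All adverse events in the case report form: does not.
- All serious events to the medical monitor within 24 h: does not.
- Unexpected serious events to the IRB: does not.
- Fatal or life-threatening serious events to FDA within 7 calendar days: does not.
- Other unexpected serious events to FDA in writing within 10 working days: depends on the grade.
- Adverse events that are not expected, to FDA within 10 working days: does not, and has no seriousness condition.

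One of six depends on the grade, and the last rule covers the same unexpected events without a causality test.

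**Step 4. What is left exposed.** Removing serious events and events leading to discontinuation leaves non-serious events in subjects who continue or complete. These subjects are confined, with adverse events monitored until discharge on the morning of Day 8 (sections 4.6.4 and 4.6.5). The last dose is on Day 7 at 0 h, so discharge comes about 24 h after it, and section 4.6 lists no later visit. The exposed group is therefore chiefly non-serious events still present at discharge. Severity is graded separately (section 4.7.3.1.3), so this group can include events graded severe.

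**The case against.** The strongest case against is that little depends on the grade, and much of it stands. A reader might infer that a downgraded event falls out of the follow-up and reporting rules altogether. The documents do not support that: seven of the nine rules above ignore causality, and the one FDA report that uses it is backed by the rule for events that are not expected. A reader might also infer that the event necessarily falls to Unlikely Related. The text does not say so; it leaves a gap.

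Headache is a tempting second example. Section 4.1.2 says "Headache, sometimes severe, is the most common adverse effect", and section 4.2.2 bars caffeine "within 24 h of check-in. Subjects must refrain from ingesting these throughout the study". But the protocol nowhere names caffeine abstinence or fasting as a cause of headache, and the fast ends with a meal begun within 2 minutes of dosing. Headache in the COVID-19 criterion counts only with a second symptom, and such subjects are excluded. The documents therefore do not show a competing cause of headache in every subject and period.

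Dizziness has limits too. The warning concerns the time of the procedure, so timing will separate some cases. The 13 plasma times in each of 4 periods give 13 × 4 = 52 draws, but a catheter may be used, so these are not 52 venipunctures.

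Finally, the double-blind placebo crossover summarizes events by treatment at onset, a comparison that needs no causality grade, and safety is not among the listed objectives. That limits the consequence. It does not repair the definition: the alternative reading of Probably Related puts the levels out of order, and the joint reading leaves the gap.

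**Conclusion.** The point holds in a limited form. As written, an event with strong timing, a plausible mechanism and a credible competing cause cannot be Possibly Related and has no clear level. Two things follow. Non-serious events that do not lead to discontinuation, chiefly those unresolved at Day 8 discharge, can lose required follow-up until they resolve or stabilize. The summaries by relationship can under-count possibly related events.

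The primary endpoint and incidence by treatment are unaffected, and reporting and follow-up of serious events are essentially so. The documents give no expected event rate, so the number of events concerned cannot be estimated.

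This rests on two assumptions: that investigators apply the definitions literally, and that the FDA rule for events not expected is read as a list of alternatives. If investigators already read Possibly Related loosely, the follow-up loss is smaller, but grading then depends on individual habit rather than on the text.

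**What to change.** Change section 4.7.3.1.4 in three places.

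1. Possibly Related: remove the no-other-explanation condition, keep the strong temporal relationship and biological plausibility, and state that another explanation may also exist. Keeping strong rather than reasonable timing preserves the distinction from Unlikely Related.
2. Probably Related: keep the no-other-explanation condition, and say whether the listed criteria are joint or alternative.
3. Not Related: limit the alternative-cause part to events clearly attributed to another cause.

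Leave the triggers in section 4.7.3.1.2 as they are, and align the guidance on the adverse event form. The cost is a few sentences of text and somewhat more non-serious events graded possibly related and followed. No change to the SAP is needed, because its summaries take the grade as recorded.

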#### **4.7.3.1.5 Pregnancy**

A serum pregnancy test will be performed for female subjects at the time points presented in the Schedules of Events (Table 8-1). If a subject becomes pregnant while on the study, this should be reported immediately to the investigator, the subject will be withdrawn from the study and the medical monitor and the subject will be instructed to follow-up with his or her personal physician. All pregnancies are to be reported as an AE and followed for outcome.

#### **4.7.3.2 Clinical Laboratory Tests**

Clinical laboratory and diagnostic screening tests will be performed at the time points presented in the Schedules of Events (Table 8-1) and will be collected in accordance with acceptable laboratory procedures. Clinical laboratory testing will be performed by Spaulding Clinical Research or Quest Diagnostics. The clinical laboratory tests that will be performed are presented in

Table 4-3. Unused clinical laboratory test samples will not be stored for future use.

**Table 4-3: Clinical Laboratory Tests and Diagnostic Screening Tests**

Hematology	Serum Chemistry	Urinalysis
Hematocrit Hemoglobin Platelet count Red blood cell count White blood cell count (with automated differential)	Alanine aminotransferase Albumin Alkaline phosphatase Aspartate aminotransferase Bicarbonate Bilirubin (total, direct, and indirect) Blood urea nitrogen Calcium Chloride Creatinine (including calculated creatinine clearance) Glucose Lactate dehydrogenase Magnesium Phosphorus Potassium Sodium Total protein Uric acid	Appearance Bilirubin Blood Color Glucose Ketones Leukocyte esterase Microscopic examination: red blood cells, white blood cells, epithelial cells, bacteria, crystals, and casts (if present) Nitrite pH Protein Specific gravity Urobilinogen
Diagnostic Screening Tests:		
Serum	Urine	Other
Serology (human immunodeficiency virus Ag/Ab Combo 1/2, hepatitis C virus antibody, and hepatitis B surface antigen) Female Subjects Only Human chorionic gonadotropin (for pregnancy)	Drug screen including: amphetamines, barbiturates, benzodiazepines, cannabinoids, cocaine, alcohol, opiates, phencyclidine, propoxyphene, and methadone	H. pylori breath test SARS-CoV2 molecular test

Clinical laboratory results will be reviewed by the investigator or designee together with data in the eCRF. Any values outside the reference range will be evaluated for clinical significance. If a value is determined to be clinically significant, the subject will be instructed to follow-up with his or her personal physician. The investigator or designee may repeat the clinical laboratory tests if deemed appropriate. The investigator will maintain a copy of the laboratory accreditation and the reference ranges for the laboratory used.

**4.7.3.3 Vital Sign Measurements**

Vital signs (blood pressure, heart rate, respiratory rate, and oral body temperature) will be measured using an automated device at the time points presented in the Schedules of Events (Table 8-1). The subject should be in a supine position, if possible, for a minimum of 5 minutes before vital signs are measured.

#### 4.7.3.4 Safety 12-lead Electrocardiograms

12-lead ECGs will be obtained with the subjects in the supine position for a minimum of 5 minutes before recording. ECGs will be overread by a physician. If an abnormality is observed, the subject will be instructed to follow-up with his or her personal physician.

#### 4.7.3.5 Physical Examinations

A complete physical examination will be performed at the time points presented in the Schedules of Events (Table 8-1).

The complete physical examination will include, but not be limited to, assessments of the head, eyes, ears, nose, throat, skin, thyroid, nervous system, respiratory system, cardiovascular system, abdomen (liver and spleen), lymph nodes, and extremities. Height, weight (without shoes and wearing the lightest possible clothing), and calculation of body mass index will be performed at Screening and check-out.

If a clinically significant abnormality is observed upon physical examination, the subject will be instructed to follow-up with his or her personal physician.

